7.2 STATISTICAL ANALYSES

- **Demographic Characteristics**

The demographic and baseline characteristics will be summarized by using descriptive statistics. Continuous variables such as age will be summarized by number of observations (n), arithmetic mean (mean), standard deviation (SD), median, minimum value (min), and maximum value (max) and Categorical variables such as menopausal status, induced menopause, family history of breast cancer and patient deceased will be presented by frequency (n) and percentage (%).

- **Initial and advance breast cancer diagnosis**

For all the patients initial diagnosis of breast cancer stages (stage 0 to stage IV) will be presented in frequency counts (n) and percentage (%). For the advance stages (stage IIIb, IIIc or IV) of breast cancer patients again locoregionally advanced or metastatic frequency counts (n) and percentage (%) will be given. For the metastatic disease, sites of metastases such as Bone, Liver, Brain, Lung, Lymph nodes and others with further segregation like single or multiple locations will be presented in frequency (n) and percentage (%).

- **Prior Therapy**

For all patient's prior therapy type (Targeted, Endocrine and Chemotherapy) will be presented by frequency count and percentage

- **Performance status**

Performance status using ECOG scale at the initiation of palbociclib treatment. Status is measured using 4 point scale from fully active to completely disable and will be summarized by frequency (n) and percentage (%).

- **Early Breast Cancer Treatment History**

Following early breast cancer diagnosis treatments received such as surgery, radiotherapy, neoadjuvant treatment, adjuvant chemotherapy, adjuvant endocrine therapy by patients will be summarized by frequency (n) and percentage (%).

- **Palbociclib Treatment**

PFIZER CONFIDENTIAL

For all the patients initial dose prescribed of palbociclib, any dose adjustments made to palbociclib and for each dose adjustment if dose reduced or increased, palbociclib was temporarily interrupted, cycle delay and reason for dose change will be summarized by frequency (n) and percentage (%). Moreover, complete summary (frequency and percentage) of all supportive therapies that patients received will be presented.

- **Advance Breast Cancer Treatment History**

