Table 3.1 Advance Breast Cancer Diagnosis by line of treatment (first line vs. second and later line)

Table 4 Prior Therapy– All Subjects

PFIZER CONFIDENTIAL

Characteristic (Unit)	Statistics	Palbociclib (N=xx)
Prior Therapy		
Targeted	n (%)	xx (xx.x)
Endocrine	n (%)	xx (xx.x)
Chemotherapy	n (%)	xx (xx.x)
Abbreviations: N = number of subjects in Palbociclib group; n = number of subjects in specified category		
Note 1: Percentages are based on the number of subjects in the Palbociclib group.		
Table 4.1 Prior Therapy by line of treatment (first line vs. second and later line)		

Table 5 Performance Status– All Subjects

PFIZER CONFIDENTIAL

Characteristic (Unit)	Statistics	Palbociclib (N=xx)
Performance Status on ECOG Scale at Palbociclib initiation		
0	n (%)	xx (xx.x)
1	n (%)	xx (xx.x)
2	n (%)	xx (xx.x)
3	n (%)	xx (xx.x)
4	n (%)	xx (xx.x)
5	n (%)	xx (xx.x)
Abbreviations: N = number of subjects in Palbociclib group; n = number of subjects in specified category; ECOG = Eastern Cooperative Oncology Group		
Note 1: Percentages are based on the number of subjects in the Palbociclib group.		
Table 5.1 Performance Status by line of treatment (first line vs. second and later line)		

PFIZER CONFIDENTIAL

Table 6 Early Breast Cancer Treatment History – All Subjects

Characteristic (Unit)	Statistics	Palbociclib (N=xx)
Neo/Adjuvant Therapy Received by Patient		
Adjuvant chemotherapy	n (%)	xx (xx.x)
Adjuvant endocrine therapy	n (%)	xx (xx.x)
Neoadjuvant treatment	n (%)	xx (xx.x)
Radiotherapy	n (%)	xx (xx.x)
Surgery	n (%)	xx (xx.x)
Don't Know	n (%)	xx (xx.x)
Abbreviations: N = number of subjects in Palbociclib group; n = number of subjects in specified category		
Note 1: Percentages are based on the number of subjects in the Palbociclib group.		
Table 6.1 Early Breast Cancer Treatment History by line of treatment (first line vs. second and later line)		

PFIZER CONFIDENTIAL

Table 7 Palbociclib Treatment – All Subjects

Characteristic (Unit)	Statistics	Palbociclib (N=xx)
Initial Dose Prescribed		
125 mg/day	n (%)	xx (xx.x)
100 mg/day	n (%)	xx (xx.x)
75 mg/day	n (%)	xx (xx.x)
Dose Adjustment		
No	n (%)	xx (xx.x)
Yes	n (%)	xx (xx.x)
Reason for Dose Adjustment		
Side effects/toxicity	n (%)	xx (xx.x)
Lack of response	n (%)	xx (xx.x)
Patient request	n (%)	xx (xx.x)
Other reasons	n (%)	xx (xx.x)
Abbreviations: N = number of subjects in Palbociclib group; n = number of subjects in specified category		

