Note 1: Percentages are based on the number of subjects in the Palbociclib group.		
Table 7.1 Palbociclib Treatment by line of treatment (first line vs. second and later line)		

PFIZER CONFIDENTIAL

Table 8 Dose Adjustment – All Subjects

Characteristic (Unit)	Statistics	Palbociclib (N=xx)
Dose Reduced		
Yes	n (%)	xx (xx.x)
Dose Resumed following interruption or cycle delay		
Yes	n (%)	xx (xx.x)
Dose Interrupted (temporarily stopped during a dose cycle)		
Yes	n (%)	xx (xx.x)
Cycle delay (the next cycle is pushed back)		
Yes	n (%)	xx (xx.x)
Combination partner therapy continued		
Yes	n (%)	xx (xx.x)
Abbreviations: N = number of subjects in Palbociclib group; n = number of subjects in specified category		
Note 1: Percentages are based on the number of subjects in the Palbociclib group.		
Table 8.1 Dose Adjustment by line of treatment (first line vs. second and later line)		

PFIZER CONFIDENTIAL

Table 9 Palbociclib Treatment- Supportive Therapies – All Subjects

Characteristic (Unit)	Statistics	Palbociclib (N=xx)
Supportive therapies		
Nutritional Support	n (%)	xx (xx.x)
Bisphosphonates	n (%)	xx (xx.x)
Antibiotics	n (%)	xx (xx.x)
Anti-anxiety drugs	n (%)	xx (xx.x)
Opioid extended release	n (%)	xx (xx.x)
NSAIDs	n (%)	xx (xx.x)
-----	-----	-----
-----	-----	-----
-----	-----	-----
Don't Know	n (%)	xx (xx.x)
Abbreviations: N = number of subjects in Palbociclib group; n = number of subjects in specified category		
Note 1: Percentages are based on the number of subjects in the Palbociclib group.		
Table 9.1 Palbociclib Treatment- Supportive Therapies by line of treatment (first line vs. second and later line)		

PFIZER CONFIDENTIAL

Table 10 Advance Breast Cancer Treatment History – All Subjects

Characteristic (Unit)	Statistics	Palbociclib (N=xx)
Time duration from Diagnosis to initiation of Palbociclib	n	xx
	Mean (SD)	xx.x (xx.xx)
	Median	xx.x
	Min, Max	xx, xx
Line of treatment		
1st line	n (%)	xx (xx.x)
2nd line	n (%)	xx (xx.x)
3rd line	n (%)	xx (xx.x)
4th or later line	n (%)	xx (xx.x)
Abbreviations: N = number of subjects in Palbociclib group; n = number of subjects in specified category		
Note 1: Percentages are based on the number of subjects in the Palbociclib group.		
Table 10.1 Advance Breast Cancer Treatment History by line of treatment (first line vs. second and later line)		

PFIZER CONFIDENTIAL

Table 11 Clinical Outcome – All Subjects

Characteristic (Unit)	Statistics	Palbociclib (N=xx)
Complete response		
Yes	n (%)	xx (xx.x)
Partial response		

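### SAP Tables 7 and 8 do not deliver the per-adjustment dose summary promised in SAP 7.2, and the resumption percentage is taken over all patients instead of those with an interruption or delay

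*SAP*

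**What the plan says.** The Palbociclib Treatment paragraph of SAP 7.2 lists what is to be reported as counts and percentages, including, in its words, "for each dose adjustment if dose reduced or increased, palbociclib was temporarily interrupted, cycle delay and reason for dose change". The dose adjustment is thus named as the thing being described, and increases are named alongside reductions.

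The shells in SAP Appendix 1 are built differently:

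- **Table 7** has one No/Yes item for any adjustment, then a list headed "Reason for Dose Adjustment" with four reasons. The list is not split by type of adjustment.
- **Table 8** has a single Yes row each for reduction, resumption ("Dose Resumed following interruption or cycle delay"), interruption, cycle delay and partner therapy ("Combination partner therapy continued"). There is no row for an increase.
- Both tables define the count as "n = number of subjects in specified category", and Note 1 reads "Percentages are based on the number of subjects in the Palbociclib group".

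SAP 7.1 has a different general rule: percentages use the number of patients suited to the analysis in question. It also requires every variable to be shown by line of treatment, which is the role of Tables 7.1 and 8.1. Dosing, dose changes, interruptions and delays form the fourth primary objective in the SAP and appear among the primary objectives in protocol section 8. Protocol Table 1 asks for reasons for treatment change where possible.

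**The concern.** Three features do not fit together.

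1. The text describes adjustments, while the shells describe patients. The number of adjustments, and the link between a reason and a type of change, do not appear in any visible table. The SAP list of tables names no other dose-adjustment output.
2. Resumption is conditional on having had an interruption or delay, but its percentage is taken over everyone. The result mixes how often events occur with what happens after them. No rule says how to classify a patient who resumed after one event but not after another.
3. SAP 7.2 includes dose increases, but Table 8 has no place for them.

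The study is purely descriptive, so these tables are the result for this primary objective. A reader of Table 8 could take a low resumption percentage to mean that few patients restarted palbociclib. A reader of Table 8.1 could take a difference between lines to be a difference in resumption.

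**Working it through.** The documents give no expected rate for any dose adjustment, so there is no stated figure to reproduce. The only input from the documents is N = 150 (SAP 4.1; the city rows of protocol Table 2 also add to 150). All rates below are assumptions, used to show how the shell behaves.

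**Resumption row.** Let p be the share of patients with an interruption or delay, and r the share of those who resume.

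- Under Note 1: printed % = (N × p × r) / N = p × r.
- Over patients with an event: (N × p × r) / (N × p) = r.

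With r = 90%:

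| p | Patients with an event | Resumed | Printed under Note 1 | Over patients with an event |
|---|---|---|---|---|
| 20% | 30 | 27 | 27/150 = 18% | 27/30 = 90% |
| 40% | 60 | 54 | 54/150 = 36% | 54/60 = 90% |
| 60% | 90 | 81 | 81/150 = 54% | 81/90 = 90% |

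The conditional denominator cannot be recovered exactly from Table 8. Interruptions (a patients) and delays (b patients) are separate rows, so the number with either is known only to lie between max(a, b) and min(a + b, N).

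**By line of treatment (Table 8.1).** Suppose p is 20% in one line and 40% in the other, with r = 90% in both. The table prints 0.20 × 0.90 = 18% against 0.40 × 0.90 = 36%. Resumption is the same in both lines, and the whole difference comes from p. Unequal p is plausible because the minimum follow-up differs by combination: 3 months with fulvestrant and 6 months with an aromatase inhibitor (protocol 9.2.1).

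**Reason rows.** The same relation holds. A reason given by 80% of adjusted patients prints as 16%, 32% or 48% of N when 20%, 40% or 60% of patients are adjusted. With one pooled list, the figure cannot be assigned to reductions, increases, interruptions or delays.

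**Repeat adjustments.** Suppose adjustments per patient follow a Poisson distribution with mean m. Expected adjustments are N × m, and expected patients with at least one are N × (1 − e^(−m)).

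| m | Adjustments | Patients with at least one | Repeats not shown |
|---|---|---|---|
| 0.3 | 45 | 38.9 | 6.1 (14%) |
| 0.6 | 90 | 67.7 | 22.3 (25%) |
| 1.0 | 150 | 94.8 | 55.2 (37%) |

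The patient count is correct in each row of this table. It simply says nothing about the repeats.

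**The case against.** The strongest reply is that Tables 7 and 8 are ordinary patient-level summaries, labelled as such, and that the SAP 7.2 sentence is too loose to commit the sponsor to event-level output: it opens with all patients and promises only counts and percentages. Much of this stands.

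- A reader might infer that repeat adjustments are miscounted. They are not. Patients with at least one reduction, interruption or delay, over N, is a valid summary.
- A reader might infer that patients without an interruption are tabulated as having failed to resume. Table 8 has no No row, so nobody is shown that way, and the printed count of resumers is unaffected.
- A reader might infer that a patient with two reasons is double counted or loses one. She can properly appear in both reason rows. Tables 3, 6 and 9 already list items of which several can apply to one patient. What is missing is a note saying so.
- A reader might infer that the partner-therapy percentage must shrink in the same way as resumption. It does so only if the item is completed solely for adjusted patients, and the shell does not say. That row is ambiguous, not shown to be wrong.
- The protocol does not itself ask for reasons by type of change. That expectation comes from SAP 7.2.

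Note 1 could also be called template wording, since it is the same under every table. But it is a stated rule, and for the resumption row it contradicts SAP 7.1. The reply also does not account for the missing increase row or for the lack of a rule on mixed outcomes.

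**Conclusion.** The point holds as a mismatch between text and shells together with a wrong base for one conditional row. Tables 7 and 8 do not give the reasons by type, the increases or the per-adjustment detail that SAP 7.2 describes. The resumption percentage under Note 1 is p × r: 18% or 36% instead of 90% under the assumed 20% or 40% with an event and 90% resuming. That relation follows from Note 1 whatever the rates are; the size of the gap depends on rates that the documents do not give. The documents do not support calling the tables miscounted.

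Two limits apply. The CRF is not available, so whether each adjustment is recorded separately is implied by SAP 7.2 but not confirmed. Some SAP output is redacted, although the dose paragraph and Tables 7 and 8 show no redaction. No test or sample size is affected. The change should be made because these tables are the reported result for a primary objective.

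**What to change.** In Table 8:

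- Keep patients with at least one reduction, interruption or delay over N, and add a row for increases.
- Base resumption on patients with an interruption or delay, print that denominator, and state how a patient with different outcomes across events is classified.
- Base partner-therapy continuation on patients with the relevant adjustment, and say which adjustments those are.

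In Table 7, split the reasons by type of adjustment and note that several may apply to one patient. Reword Note 1 in both tables, and in Tables 7.1 and 8.1, to follow the denominator rule in SAP 7.1. Where the CRF records each adjustment, add the number of adjustments by type and reason, as SAP 7.2 describes. Where it does not, amend the SAP 7.2 sentence to promise patient-level output only.

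The denominator, the notes and the mixed-outcome rule should cost only shell and programming changes, as should the increase row and the split of reasons if the CRF data identify the type of change. No extra patients or visits are needed. The adjustment-level counts depend on what the CRF captured.

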#### Patient inclusion criteria

Patients must meet all of the following inclusion criteria to be eligible for inclusion in the study:

- $\geq 18$  years old females.
- HR+/HER2- breast cancer diagnosis with confirmed metastatic or advanced disease.
- Received palbociclib with aromatase inhibitor (as prescribed by the Physician) as initial endocrine therapy in postmenopausal MBC patients or with fulvestrant in patients who have progressed on prior endocrine therapy

- Patients on LHRH agonists for ovarian function suppression in pre- or perimenopausal stage only if prescribed palbociclib with fulvestrant.
- No prior or current enrolment in an interventional clinical trial for ABC/MBC.
- Minimum of 3 months of follow up data since palbociclib with fulvestrant initiation, or minimum of 6 months of follow up data since palbociclib with aromatase inhibitor initiation.

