### 9.3 Variables

**Table 1. List of Study Variables**

Variable	Role	Data Source(s)	Operational Definition
Patient demographics	Baseline Sub-group identifier	Patient records	Age, ethnicity, weight, height, biomarker status, family history of breast cancer.
Clinical characteristics	Baseline Sub-group identifier	Patient records	Time since diagnosis, staging, node status, menopause status. ECOG/Karnofsky functional status, diagnosis for which palbociclib combination was prescribed, sites of metastases, de novo vs. recurrent disease.
Comorbid conditions	Baseline Sub-group identifier	Patient records	Comorbid conditions.
Early treatment history	Baseline Sub-group identifier	Patient records	Adjuvant treatments received since breast cancer diagnosis, time since end of adjuvant treatment, surgery/radiotherapy received.
Advanced treatment history	Baseline Sub-group identifier	Patient records	Treatments and supportive therapies received since metastatic/advanced HR+/HER2- diagnosis, duration of treatments, reasons for regimen changes.
Palbociclib combination treatment	Exposure Sub-group identifier	Patient records	Starting dose, duration of treatment, line of treatment, changes in dose, interruptions, cycle delays and discontinuations; where possible reasons for change in treatment.
Clinical outcomes	Outcomes	Patient records	Proportion progression free, ORR, TTP, PFS, patient death, 1-year and 2-year survival in all patients and within specific subgroups.

PFIZER CONFIDENTIAL

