7 STATISTICAL METHODOLOGY AND STATISTICAL ANALYSES**7.1 STATISTICAL METHODS**

Analysis of the data will be performed by the Biostatistics and Statistical Programming team. All statistical analyses will be performed using STATA 13.0 Version or higher. The SAP will be finalized before database lock.

The following standard descriptive summaries will be presented:

[figure not shown]
[figure not shown]
Descriptive statistics for continuous data:

The continuous data will be summarized using the number of observations (n), arithmetic mean (mean), standard deviation (SD), median, minimum value (min), and maximum value (max).

The number of observations (n) will be presented with no decimal place, mean and median will be presented up to one decimal place from the original value, SD up to two decimal places from the original value and (min, max) as an original value.

Descriptive statistics for categorical data:

PFIZER CONFIDENTIAL

The categorical variables will be summarized using the frequency count (n) and percentage (%) for each possible value. The frequencies will be presented up to 0 decimal places, percentage up to 1 decimal place.

All the analysed variable will be presented by the line of treatment (1st line of treatment and 2nd and later line). If data are not available, a missing category will be presented. Statistical tests, if any, will be performed at 5% level of significance. The denominator for percentages will be based on the number of patients appropriate for the purpose of the analysis.

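### Tables 8 and 8.1 report dose changes as ever/never percentages with no time base, so a difference between lines may partly reflect time on palbociclib

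*SAP*

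**What the plan says.** Dose changes, interruptions, delays and discontinuations are primary objective 4 (SAP section 2.2; protocol section 8). SAP section 7.2 plans frequencies and percentages: "for each dose adjustment if dose reduced or increased, palbociclib was temporarily interrupted, cycle delay and reason for dose change will be summarized".

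The Table 8 shell in Appendix 1 has one Yes row per event, for example "Dose Interrupted (temporarily stopped during a dose cycle"). Its denominator is patients: "Note 1: Percentages are based on the number of subjects in the Palbociclib group". The layout is then repeated by line, as "Table 8.1 Dose Adjustment by line of treatment (first line vs. second and later line"), in keeping with section 7.1: "All the analysed variable will be presented by the line of treatment (1st line of treatment and 2nd and later line").

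Protocol Table 1 lists what is collected on palbociclib: "Starting dose, duration of treatment, line of treatment, changes in dose, interruptions, cycle delays and discontinuations". No visible SAP text or shell summarises that duration, or gives cycles, events per patient or time to first change.

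On follow-up, the patient inclusion criteria require: "Minimum of 3 months of follow up data since palbociclib with fulvestrant initiation, or minimum of 6 months of follow up data since palbociclib with" an aromatase inhibitor.

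**The concern.** The chance of ever having a dose change grows with time on drug. A patient treated for 3 months and one treated for 3 years count equally in Table 8. If first-line patients stay on palbociclib longer, Table 8.1 will show more first-line patients with changes even when physicians adjust doses in the same way in both lines. A real excess in later lines could be masked for the same reason. The pooled percentage also depends on the mix of follow-up lengths in the sample, so it is hard to set beside any other source. At stake is the reading of one primary objective. No decision or error rate is involved.

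**Working it through.** **The plan's own figures.** The documents give no expected dose-change frequency or exposure time, so there is nothing of that kind to reproduce. The record total does add up (protocol Table 2): 20+10+40+20+10+10+20+20 = 150. The 7:3 split in protocol section 9.1 gives about 105 first-line and 45 later-line patients.

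**Evidence on exposure**
- Minimum follow-up is 6 months with an aromatase inhibitor and 3 months with fulvestrant.
- Protocol section 7 dates Indian approval to August 2016 (letrozole) and December 2017 (fulvestrant), so one window can open 16 months earlier. With collection ending in January 2021 as planned, follow-up cannot exceed about 53 and 37 months.
- The same section cites median PFS of 24.8 months (20.2 in the phase II trial) for initial therapy and 9.5 months after prior endocrine therapy.

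**Assumptions.** PFS stands in for time on drug, which is exponential with rate m = ln2/median: 0.0279 per month (24.8) and 0.0730 (9.5). The monthly hazard h of a first change is the same in both lines. Follow-up is capped at C months.

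P(ever changed) = h/(h+m) × [1 − exp(−(h+m)C)]

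**Constant hazard, first line vs later line (24.8 vs 9.5)**

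| h per month | C = 18 | gap | C = 36 | gap |
|---|---|---|---|---|
| 0.01 | 13.0% vs 9.3% | 3.7 | 19.6% vs 11.4% | 8.2 |
| 0.02 | 24.1% vs 17.5% | 6.6 | 34.3% vs 20.8% | 13.5 |
| 0.03 | 33.5% vs 24.6% | 9.0 | 45.3% vs 28.4% | 16.9 |
| 0.05 | 48.4% vs 36.2% | 12.2 | 60.3% vs 40.2% | 20.1 |

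Gaps are taken before rounding. With 20.2 in place of 24.8 they run from 3.1 to 10.1 points (C = 18) and 6.5 to 16.3 (C = 36).

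**Early risk only.** Replace C by 3 or 6 in the formula, and set h so that 20%, 40% or 60% would have a change if nobody stopped treatment. The gaps are 1.2, 2.2 and 3.1 points (first 3 months) and 2.1, 4.1 and 5.7 points (first 6 months).

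**Masking.** At C = 36 and h = 0.02 in first line, a later-line hazard twice as high gives 34.3% vs 34.8%: no visible difference.

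**Would events per 100 patient-months solve it?** Only if the hazard is constant. Take h = 0.06 in the first 6 months and none afterwards, in both lines, with C = 36. Mean time at risk within the first 6 months, (1 − exp(−6m))/m, is 5.52 vs 4.86 months. Mean time on drug is 22.70 vs 12.71 months. The rates are 100 × 0.06 × 5.52/22.70 = 1.46 and 100 × 0.06 × 4.86/12.71 = 2.29, a false ratio of 0.64. The crude percentages are 28.0% vs 24.8%, a ratio of 1.13. With C = 18 the false rate ratio is about 0.8.

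**Would cumulative incidence at fixed times solve it?** It removes the effect of unequal follow-up. With stopping as a competing event, it does not remove the effect of unequal discontinuation. At constant h = 0.03, the formula with C set to the time point gives 8.3% vs 7.7% at 3 months, 15.2% vs 13.4% at 6 and 25.9% vs 20.7% at 12. The residual gap is small at 3 and 6 months and about 5 points at 12.

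**The case against.** The study is descriptive. It has no hypotheses, and the SAP says only "Statistical tests, if any, will be performed at 5% level of significance", with no test specified for Table 8.1. The share of patients ever reduced is a legitimate quantity. This stands: the harm is misreading, not a wrong test. With 105 vs 45 patients, the 95% half-width for a difference is about 10 to 17 points in the scenarios examined, so most of these gaps lie within or near sampling noise.

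Three stronger readings are tempting, and the documents do not support them:
- **That time on palbociclib is known to differ greatly by line.** No section states it. The PFS and follow-up figures are by setting or partner drug, while Table 8.1 splits by line. A patient given fulvestrant after progression on earlier endocrine therapy may be first line for metastatic disease, and such mixing shrinks the contrast. Consecutive selection from an early index date also favours patients with long follow-up.
- **That the gap is as large as 52% vs 29%.** The formula gives this at 3% per month only with unlimited follow-up and a constant hazard. The approval dates rule out the first, and nothing supports the second.
- **That the plan never uses duration.** Parts of the SAP are redacted, including text in section 7.2 and material around Table 11. The statement holds only for visible text. Tables 8 and 8.1 are themselves visible and carry no time base.

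**Conclusion.** The point holds as a cheap improvement. The visible dose-change tables have no time base, and exposure is expected to be longer in first line. Under equal dosing behaviour the first-line percentage would be inflated by about 1 to 6 points if changes cluster in the first 3 to 6 months, and by roughly 4 to 20 points under a constant hazard of 1% to 5% per month with follow-up capped at 18 to 36 months. The size rests on trial PFS as a proxy for time on drug and on line tracking partner drug, which it does only partly. The documents say nothing about when dose changes occur, so neither end of the range can be excluded.

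**What to change.** - Keep n (%) in Tables 8 and 8.1.
- Add duration of palbociclib treatment (median and range), overall and by line. Protocol Table 1 already lists this variable.
- Where the eCRF holds adjustment dates, add the cumulative incidence of first reduction, first interruption and first cycle delay at fixed times from initiation, such as 3, 6 and 12 months. Treat discontinuation or death as a competing event, and censor patients still on treatment at their last record.
- Base any by-line reading on these fixed-time figures. Show the cumulative incidence of discontinuation beside them, because at 12 months unequal stopping still contributes.
- Footnote both tables: the crude percentages are not adjusted for exposure.
- Do not base the by-line reading on events per 100 patient-months. They mislead if changes cluster early, and they need event counts per patient as well as duration.

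The cost is a SAP edit and a few table rows. The cumulative incidence depends on adjustment dates having been captured, which the documents do not confirm. Without them, the duration rows and the footnote are still worth having.
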